9.1 Screening Visit (Visit 1)

Following informed consent, all consecutive patients at the recruiting centres will be screened against the inclusion/exclusion criteria outlined previously. A screening log will be maintained at each of the centres.

Potential patients will be provided with a study information sheet describing the purpose and design of the study as well as the nature of the interventions and time commitment. Written informed consent will be obtained prior to performing any study procedures. In addition, the Investigator or designee must explain to each patient, before enrollment into the study, that for evaluation of study results, the patient's protected health information obtained during the study may be shared with the study Sponsor, regulatory agencies, and the Research Ethics Board (REB)/Independent Ethics Committee (IEC). It is the Investigator's (or designee's) responsibility to obtain written permission to use protected health information per applicable regulations.

The following will be performed at the screening visit:

- Administer informed consent;
- Perform buccal swabs for GEN and E-GEN tests;
- Buccal swabs will be obtained and sent to AssureRx laboratory. A buccal swab sample will be analyzed for the pharmacogenomic testing immediately upon receipt at AssureRx. The unanalyzed buccal swabs and associated isolated DNA will be stored at AssureRx laboratory (see Appendix XVI, Part a). The sample will be de-identified, but matched to clinical data with the unique patient identification number.
- Record patient age;
- Review and record medical and psychiatric history;
- Review and record past and current psychotropic medications including response;
- Review and record past (within three months) and current concomitant non-psychotropic medications;
- Obtain vital signs;
 - Vital signs, including temperature, heart rate, sitting systolic and diastolic arterial blood pressure and radial artery pulse rate. Vital signs should be measured with the patient seated and rested at least 5 minutes.
- Perform psychiatric assessments including:
 - Mini International Neuropsychiatric Interview (MINI) for Axis 1
The MINI was developed as a short and efficient diagnostic interview to be used in clinical as well as research settings(26) (see Appendix XII). It follows DSM-IV and the ICD-10 criteria for psychiatric disorders, screening for 17 Axis I disorders, with brief suicidality and antisocial personality modules. The Axis I disorders included in the MINI were selected based upon the 12-month

prevalence reported in the Epidemiologic Catchment Area Study(27) and the National Comorbidity Survey(28). The MINI has been validated in the U.S. and Europe and administration time ranges from approximately 15-20 minutes for individuals with few positively endorsed symptoms to 20-30 minutes for individuals who meet criteria for current diagnoses.

- DSM-IV-TR criteria for MDD
The diagnostic criteria for MDD, single or recurrent are shown in Appendix XIII.
- DSM-IV-TR criteria for current substance use disorder
The diagnostic criteria for current substance use disorder are shown in Appendix XIV.
- 16-Item Clinician Quick Inventory of Depressive Symptomatology (QIDS-C₁₆)
The QIDS-C₁₆ has been extensively evaluated in patients with MDD(17, 18). Similar to the QIDS-SR₁₆, the scale assesses the nine DSM-IV criteria symptom domains for major depression: sad mood, concentration, self-outlook, suicidal ideation, involvement, energy/fatigability, sleep disturbance (4 items: initial, middle, late insomnia, and hypersomnia), appetite/weight increase/decrease (4 items), and psychomotor agitation/retardation (2 items) (see Appendix XV).
- QIDS-SR₁₆
- Collect blood for safety laboratories (hematology, and serum biochemistry).
Blood samples will be collected for the following clinical laboratory tests:
 - Hematology: hemoglobin, hematocrit, red blood cell count, white blood cell count with differential (neutrophils, lymphocytes, monocytes, eosinophils, basophils) and platelet count.
 - Serum chemistry: sodium, chloride, potassium, bicarbonate, glucose, total bilirubin, aspartate aminotransferase (AST), alanine aminotransferase (ALT), creatinine, triglycerides, cholesterol, HDL, and LDL.
 - Any abnormal laboratory value must be assessed, with written notation, by the Investigator. If an abnormal laboratory value is clinically significant, the Investigator must immediately contact the medical monitor to discuss the patient's continued eligibility in the trial.
- Collect blood for de-identified DNA and RNA pharmacogenomic research biobank;
 - An additional aliquot of blood will be collected and stored for future pharmacogenomic research at the CAMH laboratories (see Appendix XVI, Part b). The sample will be de-identified, but matched to clinical data with the unique patient identification number.
- Collect urine sample for drug screen;
 - Urine samples will be collected for drug screening (barbiturates, cannabinoids, cocaine, and opiates).

- Any abnormal blood laboratory value must be assessed, with written notation, by the Investigator. If an abnormal laboratory value is clinically significant, the Investigator must immediately contact the medical monitor to discuss the patient's continued eligibility in the trial.
- Collect information on physician's prescription (including any changes) to patient's psychotropic medication based on information available at this visit;
- Collect information on history of prior pharmacogenomics testing;
- Collect information on current or recent (30 days) enrollment in other studies;
- Evaluate patient against the inclusion/exclusion criteria.

After signing an informed consent form (ICF), the patient has 2 weeks to be evaluated for enrollment in the study. Although the Screening Visit window is 2 weeks prior to enrollment, it is preferable that the participant be assessed at least 3 days prior to enrollment since the genotype results and GeneSight report typically take 2 or 3 days to be issued after receipt of buccal swabs.

The Investigator should contact the medical monitor, as clinically necessary, if the rescheduled visit will extend the screening beyond 2 weeks.

Patients' psychotropic medication should not be modified (in terms of type and dosage) during the screening period (i.e. between the Screening and Baseline visits), except for treatment with benzodiazepines.

Each patient will be assigned a unique patient identifier (UPI). At the Screening Visit, each patient will be assigned a screening number upon signing the ICF. All screening numbers will be assigned by the site in strict numerical sequence and no numbers will be skipped or omitted (e.g., each patient will be assigned to the lowest screening number available). The UPI will be on all case report form (CRF) pages.

If at the end of the screening period the participant is found to be ineligible as per the inclusion/exclusion criteria, then the participant will become a Screen Failure and is exited from the study. The UPI will not be reused. If the participant is eligible at the end of the screening period, then the participant will be enrolled and randomized. If the participant is found to be ineligible as per the inclusion/exclusion criteria at baseline, then the subject will become a Randomization Failure.

9.2 Enrollment and Randomization

Patients who meet all the inclusion/exclusion criteria will be enrolled in the study with a 1:1:1 randomization allocation to one of three groups: GEN, E-GEN, or TAU. Investigators will be then given the results of the GEN test for the participants randomized to GEN, and of the E-GEN test for the participants randomized to E-GEN. Investigators will use the report to support their treatment decision based on this information. However, raters and participants will be blinded.

9.3 Baseline Visit (Visit 2)

Within 14 days of Screening Visit, the baseline assessment visit for the study will be completed.

Prior to any change or adjustment in antidepressant medication, the following will be evaluated and recorded:

- Psychiatric or quality of life evaluations:
 - QIDS-SR₁₆
 - HAM-D₁₇ (Central rater)
 - CGI-S (Treating clinician)
 - PHQ-9
 - GAD-7
 - EQ-5D-5L
 - SF-36
- Patient demographics;
Patients' date of birth, age, gender, ethnicity, height (without shoes), annual income, highest education, and health insurance coverage will be recorded.
- Medical and psychiatric history;
- The complete medical history will be conducted with a review of all body systems and the patient's past and concurrent illnesses, drug use (including urine drug test), alcohol use, drug allergies, and family medical history. Particular attention will be paid to past psychiatric history, in particular age at first depressive episode, frequency of relapses, response to previous treatments, and other concomitant psychiatric disorders and their treatment.

- Past and current psychotropic medications including response; The generic name of the psychotropic medication, the doses used, start and end date, as well as response to treatment (efficacy and AEs) will be recorded.
- Past (within three months) and current concomitant non-psychotropic medications (including nicotine replacement and smoking cessation medications); The generic name of the medication, the doses used, start and end date will be recorded.
- Smoking status and amounts
- Weight (without shoes, with clothes) and waist-to-hip ratio
- Changes (if any) to physician's prescription of psychotropic medication based on availability of pharmacogenomics data in GEN and E-GEN
- PIP-FQ
- UKU side effect rating scale
- FIBSER
- AEs
- Medication adjustments (including dose changes, switching, augmentation and discontinuation)
- Health resource utilization and productivity losses

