6.2.1 Inclusion Criteria

1. 18 years of age or older;
2. Suffer from a Major Depressive Episode meeting Diagnostic and Statistical Manual of Mental Disorders, Fourth Edition, Text Revision (DSM-IV-TR) criteria;
3. Have had an inadequate response within the current episode to at least one psychotropic treatment (listed in Appendix I). Inadequate response is defined as inadequate efficacy after 6 weeks of a psychotropic treatment or discontinuation of a psychotropic treatment due to adverse events (AEs) or intolerability;
4. Have each a screening and baseline score on the 16-item Clinician Quick Inventory of Depressive Symptomatology (QIDS-C₁₆) and 16-item Self-Report Quick Inventory of Depressive Symptomatology (QIDS-SR₁₆) rating scales ≥ 11 ;
5. Be able to understand the requirements of the study and provide written informed consent to participate in this study;
6. Agree to abide by the study protocol and its restrictions and be able to complete all aspects of the study, including all visits and tests.

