10.0 SAMPLE SIZE

The study will recruit participants from approximately 8-12 sites stratified into 2 clusters. CAMH will constitute one study site and a single stratified cluster. The remaining sites will constitute the second cluster. The sample size required for this study was calculated using effect size estimates drawn from a previous study conducted by Hall-Flavin et al.(11) Assuming an effect size of 0.30 in HAM-D₁₇ score favoring the treatment group, intra class coefficient between clusters of 20%, statistical power of 90%, an alpha level of 0.05, and an expected 16.7% rate of premature discontinuation (based on ongoing studies and experience with the intervention) by Week 8 (primary endpoint), a total of 570 participants (i.e., 190 per treatment arm) are required to detect the same effect in this study. Sample size calculations were determined using SAS (SAS Institute, Inc., Version 9.3, Cary, NC).

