### **3.3 Covariates**

Baseline HAM-D17 score is a covariate for the primary analysis. For secondary and exploratory analyses, the following covariates may be added to the model with baseline score: Age, Gender, Treatment, and Site Type (PCP/Psych).

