## **5 EFFICACY ANALYSIS**

### **5.1 Primary Efficacy Analysis**

The primary measure of efficacy is the percentage change from baseline to week 8 in HAM-D17. The percentage change from baseline in HAM-D17 will be analyzed using a Mixed Model for Repeated Measures (MMRM). The model will include treatment, week (4 & 8), treatment-by-week interaction, baseline HAM-D17 score, baseline HAM-D17-by-week interaction as fixed effects. Unstructured covariance between measurements at weeks four and eight, from the same patient, will be incorporated into the model. If there is a convergence issue, Toeplitz covariance will be used. The MMRM method employed here is known as Maximum Likelihood (ML) to effectively handle the missing values as discussed in Section 3.4. The p-value will be derived from the T-test for comparing two treatment arms at week 8 (treatment by week interaction term). If overwhelming evidence suggests that the normality assumption is not satisfied, complete case analyses (CCA) of the primary efficacy endpoint will be conducted for the PP population for the completers of week eight. The primary endpoint will be analyzed by fitting an analysis of covariance (ANCOVA) model which includes baseline HAMD-17 score. Robust regression method (M Estimation Method by Huber) will be used for CCA to detect potential outliers and appropriately weigh the influence of the outliers should they exist.

As a sensitivity analysis, complete case analyses (CCA) of the primary efficacy endpoint will be conducted for the PP population for the completers of Week 8. The primary endpoint will be analyzed by fitting an analysis of covariance (ANCOVA) model which includes treatment, baseline HAMD-17 score, age, and gender. If age and gender are not statistically significant, they may be dropped from the final model. Robust regression method (M Estimation Method by Huber) will be used for CCA to detect potential outliers and appropriately weigh the influence of the outliers should they exist.

The above MMRM and CCA analyses will also be conducted for the ITT population.

The primary methods for checking the normality assumption will be through graphical assessment using a Q-Q plot and histogram of the residuals. If the points for the Q-Q plot are approximately linear and if the histogram is approximately bell-shaped, the residuals will be considered normally distributed.

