## **6 SIGNIFICANCE LEVEL**

A significance level of 0.05 (2-sided) will be used. All analyses will be performed using IBM SPSS Statistics 25 and/or SAS 9.4 and/or JMP 14.

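### Baseline GAD-7 and treatment history are recorded in every arm but enter no HAM-D17 efficacy model; pre-specifying baseline GAD-7 is a near-free and probably small precision gain, not the repair of an error

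*Protocol*

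**What the plan says.** **What is collected.** Protocol 9.3 lists GAD-7 among the baseline scales, to be completed before any change in antidepressant medication. It also records each psychotropic drug with doses, dates and response, and says of the history: "Particular attention will be paid to past psychiatric history, in particular age at first depressive episode, frequency of relapses, response to previous treatments". Protocol 9.1 already records past and current psychotropic drugs with response at screening. Inclusion criterion 3 (Protocol 6.2.1) requires that patients "Have had an inadequate response within the current episode to at least one psychotropic treatment". That sets a minimum of one; neither the inclusion nor the exclusion criteria set a maximum.

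**What is modelled.** The SAP states that it supersedes the protocol's analysis plan.

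- SAP 3.3: "Baseline HAM-D17 score is a covariate for the primary analysis".
- SAP 5.1, primary model: "The model will include treatment, week (4 & 8), treatment-by-week interaction, baseline HAM-D17 score, baseline HAM-D17-by-week interaction as fixed effects".
- SAP 5.1, complete-case sensitivity ANCOVA: adds age and gender.
- SAP 5.2, secondary HAM-D17 model: adds age, gender, site type and race, any of which may be dropped if not significant.
- SAP 5.2, responder and remitter models: allow pre-specified covariates, but SAP 3.3 lists neither GAD-7 nor treatment history.

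GAD-7 otherwise appears in the SAP only as an exploratory outcome.

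**The concern.** A baseline variable that predicts outcome beyond baseline HAM-D17 would reduce residual variance if put in the model. It would narrow the standard error of the GEN versus TAU difference and allow for chance imbalance, with no extra patients. Prior treatment response and baseline anxiety are plausible candidates, both are already recorded, and the plan uses neither for HAM-D17.

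Two features of the plan make this worth raising. The primary comparison appears to have less power than the protocol states. And missing data are handled by maximum likelihood (SAP 3.4), with 16.7% discontinuation expected by Week 8; a covariate that predicted both dropout and outcome would make the missing-at-random assumption easier to accept.

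**Working it through.** **Inputs**

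- Protocol 10.0: "an effect size of 0.30 in" HAM-D17 score. This is a standardised effect with no separate SD, so SD = 1.
- Protocol 10.0: "statistical power of 90%, an alpha level of 0.05, and an expected 16.7% rate of premature discontinuation"; 190 per arm, 570 in total.
- Protocol 10.0: "intra class coefficient between clusters of 20" per cent, with no design effect or cluster size shown.
- SAP 6: "A significance level of 0.05 (2-sided) will be used".
- Assumed, because the documents give no value: R², the share of the Week 8 variance left after baseline HAM-D17 that the added covariates explain.

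**Step 1. The plan's own figure**

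n per arm = 2 × (1.960 + 1.282)² / 0.30² = 234 after rounding up.

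With dropout: 234 / (1 − 0.167) = 281 per arm, or 3 × 281 = 843 in total.

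The stated 190 and 570 are not reproduced. Treating the 20% coefficient as a variance reduction, 234 × (1 − 0.20) gives 188, which is close to 190 only if dropout is ignored; with dropout it is 226. A one-sided test without dropout gives 191, but the plan is two-sided. No variant tried that kept every stated input came within 3% of 190.

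**Step 2. Power with the planned numbers**

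Evaluable per arm = 190 × (1 − 0.167) = 158.27.

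Power = Φ(0.30 × √(158.27/2) − 1.960) = Φ(2.669 − 1.960) = Φ(0.709) = 76.1%.

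**Step 3. Effect of adding covariates**

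The residual SD becomes √(1 − R²), so power = Φ(2.669/√(1 − R²) − 1.960). The equivalent number per arm is 158.27/(1 − R²). The last column starts instead from the stated 90%: Φ(3.242/√(1 − R²) − 1.960).

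| Assumed R² | Power at 158 per arm | Equivalent extra patients per arm | Power if 90% were correct |
|---|---|---|---|
| 0 | 76.1% | 0 | 90.0% |
| 0.03 | 77.3% | 5 | 90.8% |
| 0.05 | 78.2% | 8 | 91.4% |
| 0.10 | 80.3% | 18 | 92.7% |

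**Step 4. Cost if R² is zero**

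GAD-7 and its by-week term use 2 parameters. A three-level count with its by-week terms would use 2 + 2 = 4 more, making 6 in all. GEN and TAU together have about 2 × 158 = 316 evaluable patients, so the loss is negligible.

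**Limits of these figures.** They treat 0.30 as standardised on the SD left after baseline HAM-D17. They use randomised patients less dropout, whereas the primary population is per protocol and so may be smaller. They ignore the information that the mixed model recovers from Week 4.

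**The case against.** The strongest reply is that nothing in the documents shows either variable to predict Week 8 HAM-D17 change. There is no correlation, no R² and no prior-trial result. A short pre-specified covariate list is a legitimate choice in a randomised trial. That stands, and it is why the gain is given only as a range.

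There are also reasons to expect a small R². Baseline HAM-D17 is already in the model, and its items 10 and 11 score psychic and somatic anxiety, which overlaps with GAD-7. Every patient has already had at least one inadequate response, which narrows the treatment-history variable. Both arguments limit the gain without removing it: two items are not a seven-item anxiety scale, and the number of failures has no upper limit.

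A reader might infer that treatment resistance is ready to use as a covariate and that adding it needs only new SAP wording. The documents do not support this. Protocol 9.3 lists no count of failed trials and no onset date for the current episode. Criterion 3 also counts stopping for adverse events or intolerability, so a simple count would mix intolerance with non-response.

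The choice of these two variables can also be called selective. The same visit records QIDS-SR16, PHQ-9, CGI-S, SF-36, age at first episode and relapse frequency, and nothing in the documents ranks them. Site, the randomisation stratum, is also absent from the primary model, and the documents give firmer grounds for that separate point. This argues for modesty, but not against using a scale that is already scored.

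**Conclusion.** The factual point holds: both variables are recorded in every arm and neither enters a specified HAM-D17 efficacy model. The consequence is a possible loss of precision. Under the assumed R² of 0.03 to 0.10 the gain is about 1 to 4 percentage points of power, equivalent to 5 to 18 more evaluable patients per arm. It could be close to zero.

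Two stronger readings should be avoided. The first is that the primary analysis is biased or wrong without these terms; leaving out a prognostic covariate does not bias a randomised comparison. The second is that the gap between the stated 90% and the recomputed 76% is due to the missing covariates. That gap comes from the sample-size inputs. To close it by adjustment, the residual variance would have to fall to 0.678 of its assumed value, an R² of about 0.32, and nothing in the documents suggests that.

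The case for acting is that the GAD-7 change costs almost nothing. It is an optional efficiency improvement.

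**What to change.** In SAP 3.3 and 5.1, before unblinding:

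1. Add baseline GAD-7 and its interaction with week as fixed effects in the primary mixed model, for both the PP and ITT runs.
2. Keep both terms whatever their p-values. The option in SAP 5.1 and 5.2 to drop non-significant covariates should not apply to them.
3. State a simple rule for missing baseline GAD-7, for example the mean over all arms combined, so that no patient leaves the model. SAP 3.4 covers only missing response variables.
4. Add baseline GAD-7 to the HAM-D17 response and remission models.

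GAD-7 is taken at the baseline visit, after randomisation. But it is self-rated by participants blinded to arm, before any antidepressant change, and at the same visit as the HAM-D17 score already used as a covariate. It is acceptable on the same terms.

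Add the number of inadequate responses in the current episode (1, 2, 3 or more) only with a derivation rule written and applied blind to arm. The rule should use the criterion 3 definition and the recorded drug dates and responses, and say how uncodable histories are handled.

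The GAD-7 change needs SAP wording and two model parameters. The count needs coding work and four more parameters. Neither needs new data collection, provided the recorded histories prove codable.

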9.4 Week 4 Visit (Visit 3)

Participants will return to the study centre at the end of Week 4 \pm 4 days (Visit 3) of the study. The following will be evaluated and recorded:

- Psychiatric or quality of life evaluations:
 - QIDS-SR₁₆
 - HAM-D₁₇ (Central rater)
 - PHQ-9
 - GAD-7
 - Morisky scale (med compliance)
 - BARS scale (med compliance)
- Smoking status and amounts
- Weight and waist-to-hip ratio

- Current psychotropic medication and psychotropic medication trials since last visit
- Current concomitant non-psychotropic medications (including nicotine replacement and smoking cessation medications)
- UKU side effect rating scale
- FIBSER
- AEs
- Medication adjustments (including dose changes, switching, augmentation and discontinuation)
- Health resource utilization and productivity losses

